### 3. PATIENT SELECTION

### 3.1 Eligibility Criteria

3.1.1 Patients must have histologically or cytologically confirmed adenocarcinoma of the prostate that is castration-resistant, defined as:

- A castrate serum testosterone level  $\leq 50$  ng/dL or 1.7 nmol/L
- Bilateral orchiectomy or maintenance on androgen ablation therapy with luteinizing hormone-releasing hormone (LHRH) or antiandrogen such as bicalutamide. Androgen deprivation therapy needs to be maintained throughout the study unless a patient has had orchiectomy by surgery.
- Serum PSA progression defined as two consecutive increases in PSA over a previous reference value, each measurement at least 1 week apart.

3.1.2 Progression after androgen receptor blockers (enzalutamide, apalutamide, or darolutamide) or androgen synthesis blockers (abiraterone acetate) or chemotherapy (docetaxel or cabazitaxel). There are no maximum number of prior therapies.

3.1.3 Progressive castration-resistant prostate cancer with two or more skeletal metastases identified by Tc-99m bone scintigraphy or prostate specific membrane antigen (PSMA) PET scan .

3.1.4 Patients must have self-reported moderate to severe pain at trial entry (baseline weekly average “worst pain in the past 24-hours” scores of  $\geq 4$  on an 11-point numeric rating scale [NRS], the Brief Pain Inventory – Short Form [BPI-SF] item #3 for worst pain).

3.1.5 Patients must either currently employ regular (not occasional) analgesic medication use for cancer-related bone pain or have undergone treatment with EBRT for bone pain within 4 weeks before starting study treatment.

3.1.6 Age  $\geq 18$  years. Children  $< 18$  years of age are excluded from the study as the prevalence of prostate cancer is extremely rare in this age group.

3.1.7 Patients must have a life expectancy  $\geq 3$  months.

3.1.8 ECOG performance status  $\leq 2$  (Karnofsky  $\geq 60\%$ , see Appendix A).

3.1.9 Patients must have a serum PSA value  $\geq 1$  ng/mL.

3.1.10 Patients must have adequate organ and marrow function as defined below to be eligible for the first treatment administration:

– absolute neutrophil count	$\geq 1,000/\text{mcL}$
– platelets	$\geq 100,000/\text{mcL}$
– hemoglobin	$> 10.0 \text{ g/dL}$
– total bilirubin	$\leq 2.5 \times$ institutional upper limit of normal (ULN)
– AST(SGOT)/ALT(SGPT)	$\leq 5 \times$ institutional ULN
– creatinine	$\leq 1.7 \text{ mg/dL}$

OR

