#### Classification of pain index based on diary pain intensity rating and analgesic intake

Pain response	Pain index	Diary pain rating change from baseline	Analgesic intake compared with baseline
Complete	1	Decrease $\geq 90\%$	Stable or reduced
Marked	2	Decrease $\geq 50\%$ to $< 90\%$	Stable or reduced
Moderate	3	Decrease $> 33\%$ to $< 50\%$	Stable or reduced
Minimal	4	Decrease $\geq 20\%$ or increase $< 33\%$	Stable
None	5	Decrease $< 20\%$ or increase $> 33\%$	Stable

Pain progression	6	Increase $\geq 20\%$	Stable or increased
		Decrease $<20\%$ or increase $<20\%$	Increased
		Decrease $\geq 20\%$	Increased

This pain index is derived from a combination of the following 11-point pain intensity scale and analgesic consumption categorized according to the World Health Organization (WHO) analgesic ladder.

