### 5.10.2.2.2 Timing of Assessment

Pain at baseline and analgesic use (pre-treatment, Week 0) will be measured via serial (daily) assessments in a 7-day run-in period. Patients will be considered evaluable if they complete assessments on  $\geq 4$  days within the 7-day run-in period. During treatment, pain and analgesic use will be measured every 2 weeks through Week 28, followed by routine clinic follow-up until 1 year or when patients experience new pain. Complete pain assessments via the full BPI-SF (Appendix D) will be collected at baseline, after Cycle 1, after Cycle 2, and at Week 28. Pain assessments will be halted at the patient's request or if the patient discontinues study treatment for reasons other than disease progression.

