#### 9.4.4 Overall Pain Response Rate

The rate of achievement of pain index  $\leq 3$  within 12 weeks from the first Sn-117m-DTPA will be evaluated.

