A: Sn-117m-DTPA: 20 mCi/70 kg (0.28 mCi/kg) slow IV injection over 10 min on C1D1 and C2D1

\*Patients can be retreated if pain recurs within 6 months after 16-week pain observation period

a: Follow-up visit evaluation. Every 3 months or as clinically indicated up to one year from the first dose injection or disease progression

b: Albumin, ALP, total bilirubin, bicarbonate, BUN, calcium, chloride, creatinine, glucose, LDH, sodium, potassium, total protein, SGOT [AST], SGPT [ALT].

c: Pre-treatment daily baseline pain and analgesic use for 7 days (at least 4 out of 7 days) is required before treatment initiation. Patients will be asked to report their pain at its worst in the last 24 hours and analgesic use (stable/reduced/increased) by digital version every 2 weeks through Week 28, followed by routine clinic follow up or when they experience new pain during off-visit. **A full short version of brief pain inventory (BPI) will be asked at baseline, after Cycle 1, after Cycle 2, and at Week 24.**

d: PRO-CTCAE survey items will be assessed by digital instruments. Beginning at Week 28, surveys are requested every 3 months for 6 months after the last study treatment administration.

e: Serial DTPA dosimetry scans (optional) will be obtained at 1 hour, 4 hours (or within 4-6 hours), 24 hours (or within 16-24 hours), 48 hours (or within 36-48 hours), 72 hours (or within 60-72 hours), 1 week (+/2 days), and 4 weeks (+/2 days) post-infusion. The dosimetry scan will only be performed with first cycle of injection.

f: Urine collection for urinalysis will be collected at the indicated time points or as clinically indicated to monitor for microscopic or macroscopic hematuria as part of genitourinary toxicity monitoring.

g: Imaging: Follow up tumor response will be evaluated by CT scan of abdomen and pelvis, bone scan and chest X-ray. If Chest X-ray shows abnormal or clinically symptomatic, then CT chest should be obtained. Follow-up scans at every 8 weeks will be performed as clinically indicated, per institutional standards. PSMA PET CT scan at baseline is also acceptable.

*NCI Protocol #: 10437*

*Version Date: January 10, 2022*

h: Blood collections for research during Cycles 1 and 2 should be collected on the last day of each cycle.

i: CBC and serum chemistry should be performed 1 week before the start of Cycle 2.

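### With one 24-hour rating every 2 weeks and no confirmation, a single chance low rating can set overall pain response and start its duration

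*Combined protocol and SAP*

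**What the plan says.** **Baseline.** Section 3.1.4 sets entry on a "baseline weekly average" of worst-pain scores of at least 4. Section 5.10.2.2.2 says baseline pain and analgesic use "will be measured via serial (daily) assessments in a 7-day run-in period". Study Calendar note c adds: "Pre-treatment daily baseline pain and analgesic use for 7 days (at least 4 out of 7 days) is required before treatment initiation". The average therefore rests on 4 to 7 ratings. No section separately defines the baseline value used in the pain index; the run-in average is the natural reading.

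**After baseline.** Note c says "Patients will be asked to report their pain at its worst in the last 24 hours and analgesic use", every 2 weeks through Week 28. That is one rating per time point. No section asks for several ratings per time point, an average or a confirming rating.

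**Index.** The table in 5.10.2.2.1 is titled "Classification of pain index based on diary pain intensity rating and analgesic intake". An index of 3 or below needs a fall of more than 33% from baseline with stable or reduced analgesics.

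**Endpoints.** Section 9.4.4 evaluates "The rate of achievement of pain index" 3 or below within 12 weeks of the first dose. (Objective 1.2.5 places the same endpoint at 24 weeks; one rating can decide it under either.) Section 9.4.5 runs duration from reaching index 3 or below to an index of 4 or above. Section 9.1 defines sustained response as index 3 or below reached within 12 weeks, then held for 16 weeks counted from the first time it is reached.

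**Contrast.** Section 9.4.6 defines confirmed PSA and ALP responses, with a second value about 4 or more weeks later.

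**The concern.** A single 24-hour rating varies more from day to day than a mean of 4 to 7. Under 9.4.4 a patient has six ratings by Week 12, and any one of them can make him a responder. The rule picks up the best of six chances, so day-to-day variation alone can produce responders among patients with no benefit. The same rating starts the clock in 9.4.5, so some durations would begin at a chance dip and end at the next visit.

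The same variation works the other way on the primary endpoint, where any one of eight later ratings can cancel a response. At stake are the credibility of the reported overall pain response rate and duration, and some power for the go/no-go decision.

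**Working it through.** **Counts.** Ratings at Weeks 2, 4, ..., 28: 28/2 = 14, of which 12/2 = 6 fall by Week 12. A 16-week hold spans 16/2 + 1 = 9 ratings: the qualifying one and 8 later ones.

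**What one rating must show.** At baseline 6, a rating of 4 is a fall of 2/6 = 33.3%, just past the 33% cut. At baseline 8, a rating of 6 is a fall of 2/8 = 25% and fails; 5 is a fall of 3/8 = 37.5% and passes. A 2-point dip can be enough at baseline 6, but 3 points are needed at 8.

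**False overall response, by formula.** If a patient with no change has independent chance f of a qualifying rating at each visit, the chance of at least one in six is 1 − (1 − f)^6. The last column requires two consecutive qualifying ratings among the six.

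| f | any one of six | two consecutive of six |
|---|---|---|
| 2% | 11.4% | 0.2% |
| 5% | 26.5% | 1.2% |
| 10% | 46.9% | 4.6% |
| 20% | 73.8% | 16.4% |

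**False overall response, by simulation.** Assumptions: integer ratings 0 to 10, baseline the mean of 7 days, independent days, stable analgesics, no true change, at least 60,000 simulated patients per scenario. The documents give no SD, so a range is shown.

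| | SD 1.0 | SD 1.5 | SD 2.0 |
|---|---|---|---|
| f per visit, baseline 6 | 4.1% | 11.0% | 17.3% |
| Overall response by Week 12, baseline 6 | 21% | 47% | 64–65% |
| Overall response by Week 12, baseline 8 | 4% | 23% | 42% |
| Two consecutive, onset by Week 12, confirmed by Week 14, baseline 6 | 1.5% | 8% | 16% |

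Putting f into the formula gives 22%, 50% and 68%. The simulated values are slightly lower because a patient's six comparisons share one baseline mean. The two-consecutive rule still captures 96% or more of patients whose pain truly falls and stays 58% lower (6 to 2.5).

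**Primary endpoint.** The plan's figure here is power. For p0 = 0.1, p1 = 0.3, stopping at 1 or fewer in stage 1 and rejecting the agent at 5 or fewer of 25, section 9.1 states 3.28% type I error, 80.17% power and about 55% early stopping. With 10 first-stage patients, as written, the exact values are 2.77%, 74.0% and 73.6%. The stated figures are those for 15 first-stage patients (3.28%, 80.17%, 54.9%). That is a separate matter; both are used below.

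If each later rating of a true sustained responder has independent chance q of scoring 4 or above, the response survives with probability (1 − q)^8.

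| q | survives | true 30% is seen as | power, n1 = 10 | power, n1 = 15 |
|---|---|---|---|---|
| 0 | 100% | 30% | 74.0% | 80.2% |
| 1% | 92% | 27.7% | 66% | 73% |
| 2% | 85% | 25.5% | 58% | 64% |
| 5% | 66% | 19.9% | 33% | 37% |
| 10% | 43% | 12.9% | 8% | 9% |

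In the simulation, patients with no true change essentially never gave nine qualifying ratings in a row. The error on this endpoint runs one way.

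**Averaging, for comparison.** Probability that a true constant 58% fall from baseline 6 is scored as sustained:

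| | SD 1.0 | SD 1.5 | SD 2.0 |
|---|---|---|---|
| One rating per visit | 58% | 30% | 16% |
| 7-day mean, independent days | 99% | 91% | 73% |
| 7-day mean, within-week correlation 0.3 | about 86% | about 59% | about 42% |

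**The case against.** The size rests on assumptions. No day-to-day SD is given, and baseline 6 is less favourable than baseline 8. Correlation of 0.3 between a patient's ratings lowers the single-rating false rates at baseline 6 to about 17–19%, 38–43% and 53–59%, depending on its form. A low rating counts only with stable or reduced analgesics, and all analgesics are allowed throughout (6.3.2). Overall pain response is a descriptive secondary endpoint, and all fourteen ratings are kept, so a confirmed response could be computed afterwards. All of this stands. It limits the size without removing the defect, and a confirmation rule chosen after the data are seen is weaker than one written now.

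A reader might infer more, which the documents do not support:

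- That the run-in is averaged because a single day was judged too variable. No reason is given. The word diary in the table title proves little: 5.10.2.2.1 takes the index from a cited study and uses BPI-SF item 3 as the rating.
- That the primary endpoint is made unreliable in both directions. Single ratings can only lower the sustained rate. The 10% and 30% rates are stated for that endpoint itself, so the 30% may already allow for some of the loss. Objective 1.1.1 does not say that the 16 weeks run from the first achievement; if a new window may start by Week 12, capture of the 58% fall is 68%, 41% or 25% instead of 58%, 30% or 16%.
- That daily ratings in every assessment week are required. Their benefit shrinks with within-week correlation, and they mean up to 14 × 7 = 98 ratings instead of 14.
- That noise and short-lived benefit could never be told apart. The fourteen retained ratings allow at least a later check.

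**Conclusion.** The point holds for overall pain response (9.4.4) and for the start of duration of response (9.4.5): one chance low rating, with analgesics stable or reduced, is enough. Under independent days and stable analgesics, the false-response probability by Week 12 is about 21%, 47% or 65% at baseline 6 and about 4%, 23% or 42% at baseline 8, for SD 1.0, 1.5 or 2.0. These are upper bounds with respect to analgesic use, and the SDs are assumptions.

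For the sustained endpoint the consequence is conservative: lost power, no rise in type I error, and a size that depends on how often a true responder gives a stray high rating. That part supports an option to consider and not a required change.

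**What to change.** **Recommended.** In 9.4.4, define overall pain response as pain index 3 or below at two consecutive 2-week assessments, dated at the first, with onset by Week 12 and confirmation by Week 14. Use the same definition for the start of response in 9.4.5. State how a missing second rating is handled, and align objective 1.2.5 (24 weeks) with 9.4.4 (12 weeks). This needs wording only and no new data. The cost is a lower reported overall response rate. If chance lows tend to last beyond two weeks, the rule removes fewer of them than the independent-day figures show. It does not change the primary endpoint or the end of response in 9.4.5.

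**Optional, for the sponsor to weigh.** Collect the worst-pain item on several days of each assessment week and compute the index from the mean, by the run-in rule (at least 4 of 7 days). This would reduce the power loss on the sustained endpoint, by an amount that depends on within-week correlation. The cost is patient burden, up to 98 ratings instead of 14, some of them on paper, and more missed entries.

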### 1.2 Secondary Objectives

1.2.1 To assess the safety and tolerability of Sn-117m-DTPA per CTCAE v5.0.

1.2.2 To measure Sn-117m-DTPA activity by gamma-camera dosimetry scans (serial full body planar images) obtained at 1 hour, 4 hours (or within 4-6 hours), 24 hours (or within 16-24 hours), 48 hours (or within 36-48 hours), 72 hours (or within 60-72 hours), 1 week ( $\pm 2$  days), and 4 weeks ( $\pm 2$  days) after the first Sn-117m-DTPA administration.

1.2.3 To evaluate the therapeutic efficacy of Sn-117m-DTPA at 24 weeks as measured by Prostate Cancer Working Group 3 (PCWG3) criteria.

1.2.4 To evaluate time to the first symptomatic skeletal event defined as i) the first use of external-beam radiation therapy to relieve skeletal symptoms; ii) new symptomatic pathologic vertebral or nonvertebral bone fractures; iii) spinal cord compression; or iv) tumor-related orthopedic surgical intervention.

1.2.5 To evaluate the overall pain response rate at 24 weeks.

1.2.6 To evaluate the duration of pain response defined as from the time of improvement in pain response (pain index  $\leq 3$ ) until the pain recurs.

1.2.7 To measure changes and time to progression in serum prostate-specific antigen (PSA) and serum alkaline phosphatase (ALP) levels.

1.2.8 To measure patient-reported outcomes (PROs) and adverse events (AEs) (PRO-CTCAE) captured by digital instruments.

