#### 9.4.8 Clinical Progression-Free Survival

Clinical PFS will be calculated from the time of study enrollment until disease progression, which is defined as 1) symptomatic progression (increasing pain from a metastatic lesion); 2) progression of bone lesions assessed per PCWG3 criteria; or 3) progression of soft-tissue lesions

assessed per RECIST v1.1 criteria. PSA progression without progression on bone lesions nor symptomatic is not considered as clinical progression. Clinical PFS will be censored if clinical progression is not observed.

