## 11. STUDY CALENDAR

Baseline evaluations are to be conducted within 4 weeks prior to start of protocol therapy. Scans and x-rays must be done  $\leq$  8 weeks prior to the start of therapy. In the event that the patient's condition is deteriorating, laboratory evaluations should be repeated within 48 hours prior to initiation of the next cycle of therapy.

Visit dates and scans can be within  $\pm$  7 days of planned dates. Study treatment must start within 30 days of registration.

	Pre-study	Cycle 1 (8 weeks or 56 days)					Cycle 2 (8 weeks or 56 days)					Post-treatment					Follow-up a	Off-study visit	
		W1	W2	W4	W6	W8	W1	W2	W4	W6	W8	18 weeks	20 weeks	22 weeks	24 weeks	26 weeks	28 weeks		
Sn-117m-DTPA		A					A											A*	
Informed consent	X																		
Demographics	X																		
Medical History	X																		
Pain medication**	X	X	X	X	X	X		X	X	X	X		X		X		X	X (every 3 months)	X
Physical Exam	X	X		X	X			X		X		X		X		X		X	X
Vital signs	X	X		X	X			X		X		X		X		X		X	X
Height	X																		
Weight	X	X		X	X			X		X		X		X		X		X	X
Performance status	X																	X	
CBC/diff, platelets	X	X	X	X	X	X i		X	X	X	X		X		X		X	X	X
Serum chemistry b	X	X	X	X	X	X i		X	X	X	X		X		X		X	X	X
PSA	X			X	X			X		X		X		X		X		X	X
Adverse Events		X-----X																	
Patient-reported pain intensity scale and analgesic use c	X		X	X	X	X		X	X	X	X	X	X	X	X	X	X	X	X
Patient-reported CTCAE d			X	X	X	X		X	X	X	X	X	X	X	X	X	X	X	X
Sn-117m-DTPA dosimetry (optional) e		X	X	X	X														
Urine collection for urinalysis f	X						X												

NCI Protocol #: 10437  
 Version Date: January 10, 2022

	Pre-study	Cycle 1 (8 weeks or 56 days)					Cycle 2 (8 weeks or 56 days)					Post-treatment					Follow-up a	Off-study visit	
		W1	W2	W4	W6	W8	W1	W2	W4	W6	W8	18 weeks	20 weeks	22 weeks	24 weeks	26 weeks	28 weeks		
Radiologic evaluation (CT of abdomen/pelvis and bone scan) and chest X-ray g or PSMA PET CT scan	X					X					X				X			X (every 3 months)	
Research blood for genomic whole exome sequencing (mandatory when archival tissue or slides are submitted)	X																		
Research blood for exploratory studies (optional) h	X					X h					X h				X				
Archival tissue for genomic sequencing and exploratory PLK1 stain (optional)	X																		

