Bone	
For control/relieve eliminate end points:
 

○ Record changes as new lesions or no new lesions

○ Changes in intensity of uptake alone do not constitute progression or regression

○ First schedule reassessment:

○ No new lesions: continue therapy

○ New lesions: perform a confirmatory scan 6 or more weeks later

○ Confirmatory scan:

○ No new lesions: continue therapy

○ Additional <math>\geq 2</math> new lesions: progression

○ Subsequent scheduled reassessments:

○ No new lesions: continue

○ New lesions: progression

○ For delay/prevent end points (Progression)

○ Exclude pseudo-progression in the absence of symptoms or other signs of progression

○ At least two new lesions on first post-treatment scan, with at least two additional lesions on the next scan (2+2 rule)

○ If at least two additional new lesions are seen on the next (confirmatory) scan, the date of progression is the date of the first post-treatment scan, when the first two new lesions were documented.

	

○ For all scans after the first post-treatment scan, at least two new lesions

○ Date of progression is the date of the scan that first documents the second lesion

Frequency of assessment of bone scan or other CT scans	Every 8 to 9 weeks for the first 24 weeks, then every 12 weeks

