## 12.2 Disease Progression in Soft Tissue Lesions

Patients should be re-evaluated for response/disease progression every 8 weeks for the first 24 weeks, and then every 12 weeks. No confirmatory scan is required for soft tissue lesions following initial documentation of objective response.

Response and progression in soft-tissue lesions will be evaluated in this study using the new international criteria proposed by the revised Response Evaluation Criteria in Solid Tumors (RECIST) guideline (version 1.1) [Eur J Ca 45:228-247, 2009]. Changes in the largest diameter (unidimensional measurement) of the tumor lesions and the shortest diameter in the case of malignant lymph nodes are used in the RECIST criteria.

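### Calendar note g makes the 8-weekly scans discretionary, against its own grid row and Section 12, so the timing of the imaging behind PFS and the 24-week result is not secured

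*Combined protocol and SAP*

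**What the plan says.** **Fixed times.** The PCWG3 table in Section 12.1.1 sets bone scans and CT at "Every 8 to 9 weeks for the first 24 weeks, then every 12 weeks". Section 12.2 says "Patients should be re-evaluated for response/disease progression every 8 weeks for the first 24 weeks, and then every 12 weeks". The Section 11 grid row "Radiologic evaluation (CT of abdomen/pelvis and bone scan) and chest X-ray" is marked at pre-study, Cycle 1 week 8, Cycle 2 week 8 and week 24, then every 3 months. The calendar preamble gives the tolerance: "Visit dates and scans can be within" 7 days either side of plan.

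**Discretionary times.** Note g, attached to that row, says "Follow-up scans at every 8 weeks will be performed as clinically indicated, per institutional standards". Note a describes follow-up visits as "Every 3 months or as clinically indicated up to one year from the first dose injection or disease progression", and Section 6.5 has similar wording with a 12-month limit from the first dose.

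**What uses the scans.** Secondary objective 1.2.3 is "To evaluate the therapeutic efficacy of Sn-117m-DTPA at 24 weeks as measured by Prostate Cancer Working Group 3 (PCWG3) criteria". Clinical PFS (Section 9.4.8) counts symptomatic progression, "progression of bone lesions assessed per PCWG3 criteria", and RECIST 1.1 progression in soft tissue. Section 9.4 censors patients without observed clinical progression at the last assessment and does not say which assessment is meant. Section 9 has no rule for a missed scan in PFS.

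**The concern.** Clinical PFS already counts symptomatic progression as an event, with or without a scan. What scheduled imaging mainly adds is progression found in patients who feel well, and a scan in such a patient is the easiest to omit under a clinical-indication rule. A patient with new complaints may be scanned sooner. The time of assessment would then carry information about the patient's state, and PFS would drift towards a symptom endpoint that overlaps with the primary pain endpoint. The reference to local standards adds variation between sites.

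Three results are exposed: the date of progression in clinical PFS, the classification of bone progression under the 2+2 rule, and progression status at week 24. A scan that was not done cannot be recovered at analysis.

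**Working it through.** **1. Do the passages conflict?** The plan states no figure on this point, so the check is of the text.

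| Place | Timing to week 24 | After week 24 | Discretion |
|---|---|---|---|
| Section 12.1.1 table | every 8–9 weeks | every 12 weeks | none |
| Section 12.2 | every 8 weeks | every 12 weeks | none |
| Section 11 grid row | weeks 8, 16 (Cycle 2 week 8: 8 + 8), 24 | every 3 months | none, ±7 days |
| Section 11 note g | every 8 weeks | not stated | clinical indication, local standards |

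Up to week 24 the first three agree within the 7-day window. Note g does not.

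**2. Could note g mean only extra scans?** An 8-weekly rhythm exists in the plan only during the first 24 weeks. The sentence therefore most naturally describes the scans at weeks 8, 16 and 24. The same note uses follow-up for tumour evaluation in general and mentions baseline separately, which also suggests that follow-up here means after baseline.

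**3. Does a skipped scan change more than the date?** Under Section 12.1.1, two new bone lesions on the first post-treatment scan need at least two more on the next scan. On any later scan, two new lesions are enough. Take a patient with no new lesions at week 8 and two at week 16:
- Week 8 scan done: progression at week 16.
- Week 8 scan skipped: week 16 becomes the first post-treatment scan, and progression is declared only if two further lesions appear on the next scan.

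The same disease course can be classified differently. If weeks 8 and 16 are both skipped, two new lesions at week 24 await a scan about 3 months later before the 24-week status is settled.

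**4. Illustration of size.** Every input is an assumption: exponential time to radiographic progression; symptoms following with a median lag of 8 or 12 weeks; progression detected at symptom onset if no scan found it first; scheduled scans at weeks 8, 16, 24, 36 and 48; the 2+2 rule not modelled. Paired values are for lags of 8 and 12 weeks.

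| True median | Scheduled scans done in symptom-free patients | Detected by week 24 | Median PFS, censored at week-48 visit | Median PFS, censored at last scan |
|---|---|---|---|---|
| 16 wk | all | 64.7% | 16 | 16 |
| 16 wk | half | 57.1 / 55.2% | 24 / 24 | 24 / 24 |
| 16 wk | none | 41.9 / 33.7% | 28.5 / 34 | 22.5 / 24.5 |
| 24 wk | all | 50.0% | 24 | 24 |
| 24 wk | half | 43.5 / 42.0% | 32.5 / 36 | 30.5 / 32.5 |
| 24 wk | none | 31.3 / 25.1% | 37 / 42.5 | 24.5 / 26.5 |
| 36 wk | all | 37.0% | 36 | 36 |
| 36 wk | half | 31.9 / 30.7% | 44.5 / 48 | 37.5 / 39 |
| 36 wk | none | 22.6 / 18.0% | not reached | 26 / 27.5 |

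Fewer scans always lower the proportion detected by week 24. The median usually rises. It falls below the truth only in the extreme case of no scans in symptom-free patients, a true median of 36 weeks and censoring at the last scan. There, patients without an event have no scan and leave the risk set almost at time zero. The censoring definition thus decides much of the size and, at the extreme, the direction.

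**The case against.** No passage gives note g precedence. Three fixed statements stand against one loose sentence, and a site that follows the grid will scan on time. Follow-up is also the name of a calendar column, so optional extra scans there are a conceivable reading. The affected endpoints are secondary and summarised descriptively in one arm of 25. The primary pain endpoint and the two-stage rule use no scans, and no between-arm bias is possible. Symptomatic progression counts without a scan, which dilutes any effect on PFS. For the response rate, Section 9.4.2 counts an unobserved response as negative.

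Most of this stands and limits the point. The optional-scan reading is weak for the reason in step 2, and the rule in Section 9.4.2 does not cover PFS or progression status at week 24.

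A reader might infer three stronger claims:
- **That note g overrides the schedule.** The documents show a conflict without an order of precedence.
- **That PFS is overstated by about 4 weeks.** This takes mean detection delay as half the scan interval: 16/2 − 8/2 = 4 weeks if every second scan is skipped. That skipping pattern is assumed, the sum ignores the 12-week interval after week 24, and earlier scans in symptomatic patients would pull the other way.
- **That bone progression could no longer be dated.** Section 12.1.1 still dates confirmed progression to the first post-treatment scan. Irregular scans make the date coarser and can shift which rule applies.

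**Conclusion.** The contradiction is real and can be seen from the text alone: note g conflicts with its own grid row and with Sections 12.1.1 and 12.2. The bias is conditional on sites following note g. The link to symptoms is the natural meaning of a clinical-indication rule, but note g does not mention symptoms. Neither size nor direction can be derived from the documents, because they state no PFS assumption and leave the last assessment undefined; the figures in the working are illustrations. The consequence is confined to secondary results: clinical PFS, bone progression under the 2+2 rule and the 24-week PCWG3 result. It matters for absolute PFS and for any comparison with outside data. It should be corrected because the wording is easy to change and unperformed scans cannot be replaced.

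**What to change.** 1. In note g, delete the closing qualification (clinical indication and local standards), so that the note matches the grid row and Section 12 within the existing one-year follow-up limit of note a and Section 6.5.
2. State that clinically indicated scans are additional to the scheduled ones and do not replace them.
3. Reconcile the clinical-indication alternative in note a and Section 6.5 in the same way, for the imaging used in PFS.
4. In Section 9.4, define the last assessment for PFS censoring as the last adequate disease assessment, and state how missed scans are handled.

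The cost is a wording amendment. It adds no scans beyond those the calendar already marks. The downside is that sites lose local discretion over those scans.
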